6.1 Estimate of sample size

The spectrum disease of optic neuromyelitis is a rare disease, and this study is an exploratory study. Referring to previous studies, the sample size of this topic is 20 Example.

6.2 Random grouping method

Use a simple randomization method to input the estimated sample content. SPSS V.25.0 Statistical software to obtain order numbers, random seed numbers and grouping results. Then make a random card and seal it in an opaque envelope. Before preparing to start the clinical trial, the serial number will be used according to the order in which the subjects were included in the study, the order number on the corresponding envelope will be opened, and then grouped according to the prompts on the random card. The whole process ensures randomness and secrecy and reduces the bias of researchers.

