5.1 Selection Criteria

1 Accord with 2021 Diagnostic criteria for optic poliomyelitis genealogical diseases in China's Guidelines for the Diagnosis and Treatment of optic Neurospinal Myelitis Gene Diseases;

2 NRS \geq 4 Score;

3 Patients use stable doses of biotherapy and/or strong loose, before joining the group 30 There is no adjustment plan within the day;

4 Patients before joining the group 30 No standard drug combinations for pain treatment, including antiepileptic drugs, antidepressants or opioids, were adjusted within the day.

5 The patient or the patient's family sign informed consent.

6 18-80 Year-year-old patient.

5.2 Exclusion criteria:

1 Patients participating in other clinical studies;

2 Patients with low cognitive or mental ability.

3 People who are pregnant, breastfeed or plan to get pregnant during the study;

4 People with serious diseases related to the heart, liver, kidney or hematopoietic system.

5 Patients with diabetic peripheral neuropathy.

5.3 Exclusion criteria:

Incorrectly included in the case;

Subjects took drugs that affected the relevant indicators of this study without authorization;

5.4 Fall off standard:

The subjects failed to complete the treatment as required by the researchers;

The subjects did not cooperate with the arrangement for personal reasons, and the researchers believed that the patient had poor compliance and was not suitable for research;

The subjects withdrew from the study on their own.

6. Sampling estimation and grouping method

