6.3 Blind law

The study includes the blind design of patients and evaluators. Only acupuncture operators know. Intervention to be used. The treatment was carried out according to the individual's schedule, so no patient had any contact with other patients in the study. In addition, all patients agree not to contact other participants and avoid talking about their treatment.

7. Interventions

This study is divided into 2 The group is the electric needle group and the false needle group respectively. The place of acupuncture treatment is Department of Neurology, Dade Road Hospital, Guangdong Provincial Hospital of Traditional Chinese Medicine. Every week 2 Times, every time 30 Minutes of electric needles (true or false), continuous 1 Months in total 8 Times (the course of treatment is 30 Oh, my God).

1· Basic treatment and emergency plan

Before starting the designated treatment plan, the patient Accepted NMOSD Guidelines for the remission period (hormonal combined immunosuppressants (immunosuppressants include thiopurine, medicophenol ester or rithitoximab)) and/Accepted NMOSD Guidelines for patients with pain (pribalin, barclofen or

gabapentine), basic treatment during the study and guidelines for patients before grouping. In the next stage of the study, all patients will start their designated treatment plan. (Electric needle) This point in time is set to 1 Day, the treatment period is 30 Oh, my God. Patients record the daily intake and intensity of analgesic drugs required. (NRS) Standardized patient diary of pain parts.

2· Test group: electric needle group

Take acupuncture points: three miles of both feet (ST36), Sanyin sex (SP6), Hegu (LI4) and Quchi (LI11), insert the needle, insert the ninth needle into the seal hall (EX-HN3)

Acupoint location reference 2006 National standards of the People's Republic of China (GB/T12346-2006 Name and Positioning of Acupoints.

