(1) The doctor will ask, record the medical history and the results of previous examinations, conduct a comprehensive physical examination of you, and the nurse will collect the patient. 3ml Blood routine, biochemical, liver function, IL6, TNF- α Examine and take blood samples, tongue coating samples and feces samples, and collect demographic information of subjects through the inpatient medical record system.

(2) Perfect EDSS, NRS Scales, MPQ Pain scale, SDS Depression Scale, SAS Anxiety Scale, SF-36 Quality of life scale.

(3) Perfect and collect head, neck and chest MR Scan and enhance relevant data to improve fMRI Check and collect relevant data.

2. Treatment period:

The electroacupuncture group will be treated with electroacupuncture on the basis of immunotherapy and basic analgesia, and the control group will receive false acupuncture treatment on the basis of immunotherapy and basic analgesia. Every week 2 Times, every time 30 Minutes of electric needles (true or false), continuous 1 Months in total 8 Times (the course of treatment is 30 Oh, my God). Patients fill in a pain diary every day, and the treatment is carried out by the same acupuncturist. The manufacturer and use of acupuncture acupuncture needles, fake acupuncture and electroacupuncture instruments are consistent.

3. Eighth post-treatment visit (group No. 28 ± 3 Day):

(1) Patients collected by nurses 3ml The blood is routinely tested for blood, biochemical and liver function, and blood samples, tongue coating samples and feces samples are retained.

(2) Perfect EDSS, NRS Scales, MPQ Pain scale, SDS Depression Table, SAS Anxiety Scale, SF-36 Quality of life scale.

(3) Perfect fMRI Check and collect relevant data.

In this study, blood samples, tongue coating specimens and fecal samples were used to explore. NMOSD The relevant mechanism of pain in patients and the mechanism of electroacupuncture in the treatment of pain in patients with optic neuromyelitis spectrum diseases, all samples will be frozen in the Biological Resources Center of Guangdong Provincial Hospital of Traditional Chinese Medicine and preserved. 3 The sample was destroyed after the study. All samples are only used for this study, and your relevant personal information will not be made public. Researchers, personnel of the Bioresource Center and the Ethics Committee will be allowed to have access to these samples, and

subjects can request withdrawal from the reservation or research of the sample at any time.

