[figure not shown]
9. Outcome evaluation indicators

Main evaluation indicators: NRS

Pain sheet rating

Secondary evaluation indicators: EDSS、MPQ Rating, SAS Anxiety Scale, SDS Depression Scale, SF-36 Quality of life scale, IL6、TNF- α 、fMRI Indicators.

10. Technology roadmap

11.2.1 Common adverse acupuncture events/Reaction and treatment: Acupuncture has adverse reactions such as hematoma, stagnation needle, halo needle, etc.

1) Spend money/Hematoma: During acupuncture and acupuncture, local bleeding caused by puncture of blood vessels./Hematoma. Mild bleeding/Of Patients with hematoma can use disinfectant cotton swabs or cotton balls for local compression to stop the bleeding without special treatment. Moderate and severe bleeding/Patients with hematoma should be based on their bleeding./Take corresponding measures to the degree of hematoma, first stop the bleeding to prevent the increase of local swelling, carry out local anti-inflammatory treatment, and ask a surgeon to assist in dealing with it.

2) Stagnation needle: When acupuncture the stagnation needle, you should first relax the local tense muscles, and gently take the needle. Do not pull it hard. It can be opened next to the stagnant needle. 2 Enter the needle inch by inch, and then take out the stranded acupuncture needle. Severe needle stagnation should be assisted by a surgeon.

3) Needle halo: When the patient pricks the needle with acupuncture, he should quickly take out the needle and let the patient lie flat, lower his head, cushion his footsteps, and moxibustion his Baihui acupuncture point. After the patient's halo needle situation is slightly relieved, he can be ordered to drink a little warm boiled water. If the patient's needle is serious and he or she can't wake up, it should be treated according to syncope.

4) Infection: When there is redness, swelling and heat pain in the acupuncture area, the patient's affected part is told to rest and move less to reduce the spread of pain and inflammation, raise the limbs, promote reflux, reduce swelling, do not squeeze the affected part, and carry out local anti-inflammatory treatment. If necessary, you should ask a surgeon to assist in dealing with it.

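### If the simple randomisation in section 6.2 means 20 independent 1:1 draws, it costs on average one effective patient in 20; a concealed permuted 10 + 10 list would avoid this

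*Protocol*

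**What the plan says.** Section 6.1 gives the size without a calculation: "Referring to previous studies, the sample size of this topic is 20 Example". It calls the disease rare and the study exploratory.

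Section 6.2 names the allocation method: "Use a simple randomization method to input the estimated sample content". The software is SPSS, used to "obtain order numbers, random seed numbers and grouping results". The cards go into sealed opaque envelopes that are opened in order of inclusion, and the section closes with its aim: "The whole process ensures randomness and secrecy and reduces the bias of researchers". Section 7 confirms two groups. No ratio, arm totals, blocks or other restriction appears in the readable text. A figure not shown stands just before section 9, near the heading "10. Technology roadmap", and might carry numbers per arm.

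Two statements bear on the remedy. On who is unblinded, section 6.3 says "Only acupuncture operators know". Section 8, under the treatment period, says "the treatment is carried out by the same acupuncturist".

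**The concern.** Simple randomisation usually means an independent draw for each patient. With 20 patients, nothing then holds the arms near 10:10. A two-group comparison is most precise with equal arms, so an uneven split spends patients without gaining the matching information.

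Only precision is at stake. It still deserves attention because the disease is rare, the total is small, the trial is run once, and section 12 plans between-group comparisons with 95% confidence intervals. The remedy needs no extra patients, visits or staff.

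**Working it through.** **Inputs.** N = 20 (section 6.1); two arms (section 7); simple randomisation (section 6.2). Assumed, because the protocol does not state them: independent draws with probability 0.5, equal SD in both arms, and a two-sided 0.05 test. No power, effect size or SD is given, so there is no sample size calculation to reproduce.

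**Expected loss.** Let n1 follow Binomial(20, 0.5) and n2 = 20 − n1. Effective N = 4·n1·n2/20. Since E[n1·n2] = 20 × 19/4 = 95, expected effective N = 4 × 95/20 = 19.0, a mean loss of 1.0. SE inflation for a given split is √(20/effective N) − 1. Averaged over splits with both arms non-empty, it is 2.8%.

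**Spread.** Each probability is the number of lists with that split divided by 2^20.

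| Split | Probability | This or worse | Effective N | SE inflation |
|---|---|---|---|---|
| 10:10 | 17.6% | 100% | 20.0 | 0% |
| 9:11 | 32.0% | 82.4% | 19.8 | 0.5% |
| 8:12 | 24.0% | 50.3% | 19.2 | 2.1% |
| 7:13 | 14.8% | 26.3% | 18.2 | 4.8% |
| 6:14 | 7.4% | 11.5% | 16.8 | 9.1% |
| 5:15 | 3.0% | 4.1% | 15.0 | 15.5% |

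Half of all trials lose 0.5% or less in standard error. About one in nine loses 9.1% or more.

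**Power.** Noncentral t with 18 degrees of freedom and noncentrality d·√(n1·n2/20), for 10:10 against the average over splits:

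| Assumed effect (SD) | 10:10 | Independent draws | Loss (points) |
|---|---|---|---|
| 0.5 | 18.5% | 17.8% | 0.7 |
| 0.8 | 39.5% | 37.9% | 1.7 |
| 1.0 | 56.2% | 54.0% | 2.2 |
| 1.2 | 71.8% | 69.5% | 2.3 |
| 1.5 | 88.7% | 86.9% | 1.8 |
| 2.0 | 98.8% | 98.3% | 0.5 |

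**With a permuted 10 + 10 list.** Effective N = 4 × 10 × 10/20 = 20, a loss of zero when all 20 are randomised and analysed.

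**Withdrawals.** Section 5.4 allows for them without giving a rate. With assumed independent dropout of 10%, expected effective N is 17.9 from a 10 + 10 start and 17.0 from independent draws. At 20% dropout it is 15.8 and 15.0.

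**Early stop.** If recruitment ended at 14, 16 or 18 (assumed), the arms would differ by 4 or more in 42%, 45% and 48% of trials under independent draws. The 10 + 10 list gives 14%, 9% and 0%.

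**Predictability of the 10 + 10 list.** Someone who tracks earlier assignments and always bets on the arm that is behind expects 12.3 correct guesses of 20, against 10.0 under independent draws. For someone who also knows the totals, the chance that the last r assignments are already determined is 2·C(20−r, 10)/C(20, 10). Summed over r = 1 to 10, this gives 1.8 assignments on average.

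**The case against.** The strongest reply is that the text does not establish the condition. The planned number is entered and SPSS returns a whole list with groups, which fits a list cut into two tens as well as independent draws. The wording is a rough translation, so the term may not be a deliberate technical choice, and the figure not shown may state arm sizes. This stands, and it is why the loss is put conditionally.

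The effect is also small: 74% of trials would lose 2.1% or less in standard error, and an exploratory study without a power target breaks no promise. This stands too.

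The objection to the remedy is serious. Section 6.2 aims at secrecy, and one acupuncturist who knows the allocations treats everyone. Withholding the list does not help against that person, who has seen every earlier assignment and would read the arm totals in the amended section. Full unpredictability at the cost of about one effective patient is a defensible choice. What answers this is keeping that person away from enrolment decisions.

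A reader might infer that simple randomisation biases the trial or makes it invalid. It does neither. A reader might also infer that a patient's worth of information is certainly lost, but the protocol does not show which kind of list was made.

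**Conclusion.** The point holds conditionally, as an inexpensive improvement to consider. Under independent 1:1 draws the plan gives up one effective patient in 20 on average, and the loss is skewed towards a minority of badly split trials. If the list already forces 10 + 10, nothing is lost and the term used in section 6.2 is simply the wrong one. The power figures rest on assumed effects, since the protocol states none. The advantage of a balanced start persists under the assumed dropout rates and early stops, although uneven dropout or early stopping can still unbalance the arms.

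**What to change.** First establish how the SPSS list was made and whether any envelope has been opened. The protocol is version 6.0 of 2022.03.01, and section 15 schedules trial conduct from February 2022, so the documents do not settle this.

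- **No envelope opened and totals not fixed:** state 1:1 allocation in section 6.2 and replace simple randomisation with one pre-generated permuted list of 10 electroacupuncture and 10 sham assignments, in the same sealed opaque envelopes.
- **List already 10 + 10:** change only the wording, to say so.
- **Envelopes already in use:** record in section 6.2 how the existing list was generated.

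With a 10 + 10 list, also state that the acupuncturist takes no part in screening or enrolment decisions, and that those who enrol see neither the list nor earlier assignments.

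The cost is at most one regenerated list and a few sentences, plus the separation of roles. The modest predictability shown above remains for anyone who knows past allocations, and the sponsor should accept it knowingly.

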6.3 Blind law

The study includes the blind design of patients and evaluators. Only acupuncture operators know. Intervention to be used. The treatment was carried out according to the individual's schedule, so no patient had any contact with other patients in the study. In addition, all patients agree not to contact other participants and avoid talking about their treatment.

7. Interventions

This study is divided into 2 The group is the electric needle group and the false needle group respectively. The place of acupuncture treatment is Department of Neurology, Dade Road Hospital, Guangdong Provincial Hospital of Traditional Chinese Medicine. Every week 2 Times, every time 30 Minutes of electric needles (true or false), continuous 1 Months in total 8 Times (the course of treatment is 30 Oh, my God).

1· Basic treatment and emergency plan

Before starting the designated treatment plan, the patient Accepted NMOSD Guidelines for the remission period (hormonal combined immunosuppressants (immunosuppressants include thiopurine, medicophenol ester or rithitoximab)) and/Accepted NMOSD Guidelines for patients with pain (pribalin, barclofen or

gabapentine), basic treatment during the study and guidelines for patients before grouping. In the next stage of the study, all patients will start their designated treatment plan. (Electric needle) This point in time is set to 1 Day, the treatment period is 30 Oh, my God. Patients record the daily intake and intensity of analgesic drugs required. (NRS) Standardized patient diary of pain parts.

2· Test group: electric needle group

Take acupuncture points: three miles of both feet (ST36), Sanyin sex (SP6), Hegu (LI4) and Quchi (LI11), insert the needle, insert the ninth needle into the seal hall (EX-HN3)

Acupoint location reference 2006 National standards of the People's Republic of China (GB/T12346-2006 Name and Positioning of Acupoints.

Operation process: The patient's position is supine. For acupuncturists 75% After disinfecting the acupoints on both sides of your hands and the subject, the double-sided acupuncture points will be covered with foam pads (1*1*1cm³). Acupuncture point adoption 0.25 × 0.25mm The disposable sterile acupuncture needle passes through the hollow tube and punctures into the acupuncture point through the foam adhesive pad. Acupoints, insertion angle and insertion depth are based on the references in the classic literature of traditional Chinese medicine. After taking the needle, the subjects will feel sour, numb and swollen in the local place. Connect the two electrodes of the electroneedle to the needle handle of the same limb acupuncture point., There is no positive or negative difference., Note that the metal surfaces of the two electrodes cannot be leaning against each other. Needle parameters: select sparse waves, The frequency is set to 4Hz The stimulation intensity is based on the patient's tolerance, and the needle retention time is 30 Minutes.

Control group: false needle group

Acupuncture points: acupoints used in the electric needle group Horizontal side 1cm Pay attention to avoiding traditional Chinese medicine. 14 Any corresponding area in the meridian.

Acupoint location reference 2006 National standards of the People's Republic of China (Generation B/T12346-2006 Name and Positioning of Acupoints.

Operation process: The patient's position is supine. For acupuncturists 75% After disinfecting the acupoints on both sides of your hands and the subject, the double-sided acupuncture points will be covered with foam pads (1*1*1cm³). All acupuncture points are used. 0.25 × 0.25mm The disposable sterile acupuncture needle passes through the hollow tube and punctures into the acupuncture point through the foam adhesive pad. The insertion of the needle is shallower (less than 0.2cm), it has a similar pain when a normal needle pricks into the needle. Connect the two electrodes of the electroneedle to the needle handle of the same limb acupuncture point., There is no positive or negative difference., Note that the metal surfaces of the two electrodes cannot be leaning against each

other. Needle parameters: select sparse waves, The frequency is set to 4Hz, the stimulation intensity is 0mA, the retention time is 30 Minutes.

8. Research steps

1. Screening period:

(1) The doctor will ask, record the medical history and the results of previous examinations, conduct a comprehensive physical examination of you, and the nurse will collect the patient. 3ml Blood routine, biochemical, liver function, IL6, TNF- α Examine and take blood samples, tongue coating samples and feces samples, and collect demographic information of subjects through the inpatient medical record system.

(2) Perfect EDSS, NRS Scales, MPQ Pain scale, SDS Depression Scale, SAS Anxiety Scale, SF-36 Quality of life scale.

(3) Perfect and collect head, neck and chest MR Scan and enhance relevant data to improve fMRI Check and collect relevant data.

2. Treatment period:

The electroacupuncture group will be treated with electroacupuncture on the basis of immunotherapy and basic analgesia, and the control group will receive false acupuncture treatment on the basis of immunotherapy and basic analgesia. Every week 2 Times, every time 30 Minutes of electric needles (true or false), continuous 1 Months in total 8 Times (the course of treatment is 30 Oh, my God). Patients fill in a pain diary every day, and the treatment is carried out by the same acupuncturist. The manufacturer and use of acupuncture acupuncture needles, fake acupuncture and electroacupuncture instruments are consistent.

3. Eighth post-treatment visit (group No. 28 ± 3 Day):

(1) Patients collected by nurses 3ml The blood is routinely tested for blood, biochemical and liver function, and blood samples, tongue coating samples and feces samples are retained.

(2) Perfect EDSS, NRS Scales, MPQ Pain scale, SDS Depression Table, SAS Anxiety Scale, SF-36 Quality of life scale.

(3) Perfect fMRI Check and collect relevant data.

In this study, blood samples, tongue coating specimens and fecal samples were used to explore. NMOSD The relevant mechanism of pain in patients and the mechanism of electroacupuncture in the treatment of pain in patients with optic neuromyelitis spectrum diseases, all samples will be frozen in the Biological Resources Center of Guangdong Provincial Hospital of Traditional Chinese Medicine and preserved. 3 The sample was destroyed after the study. All samples are only used for this study, and your relevant personal information will not be made public. Researchers, personnel of the Bioresource Center and the Ethics Committee will be allowed to have access to these samples, and

subjects can request withdrawal from the reservation or research of the sample at any time.

[figure not shown]
9. Outcome evaluation indicators

Main evaluation indicators: NRS

Pain sheet rating

Secondary evaluation indicators: EDSS、MPQ Rating, SAS Anxiety Scale, SDS Depression Scale, SF-36 Quality of life scale, IL6、TNF- α 、fMRI Indicators.

10. Technology roadmap

11.2.1 Common adverse acupuncture events/Reaction and treatment: Acupuncture has adverse reactions such as hematoma, stagnation needle, halo needle, etc.

1) Spend money/Hematoma: During acupuncture and acupuncture, local bleeding caused by puncture of blood vessels./Hematoma. Mild bleeding/Of Patients with hematoma can use disinfectant cotton swabs or cotton balls for local compression to stop the bleeding without special treatment. Moderate and severe bleeding/Patients with hematoma should be based on their bleeding./Take corresponding measures to the degree of hematoma, first stop the bleeding to prevent the increase of local swelling, carry out local anti-inflammatory treatment, and ask a surgeon to assist in dealing with it.

2) Stagnation needle: When acupuncture the stagnation needle, you should first relax the local tense muscles, and gently take the needle. Do not pull it hard. It can be opened next to the stagnant needle. 2 Enter the needle inch by inch, and then take out the stranded acupuncture needle. Severe needle stagnation should be assisted by a surgeon.

3) Needle halo: When the patient pricks the needle with acupuncture, he should quickly take out the needle and let the patient lie flat, lower his head, cushion his footsteps, and moxibustion his Baihui acupuncture point. After the patient's halo needle situation is slightly relieved, he can be ordered to drink a little warm boiled water. If the patient's needle is serious and he or she can't wake up, it should be treated according to syncope.

4) Infection: When there is redness, swelling and heat pain in the acupuncture area, the patient's affected part is told to rest and move less to reduce the spread of pain and inflammation, raise the limbs, promote reflux, reduce swelling, do not squeeze the affected part, and carry out local anti-inflammatory treatment. If necessary, you should ask a surgeon to assist in dealing with it.

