To explore the treatment of optic
neuromyelitis with
electroacupuncture(**NMOSD**)The efficacy and
mechanism of pain in patients

Project Source: Postgraduate Project

Research Unit: Guangdong Provincial Hospital of
Traditional Chinese Medicine

Head of Research: [name], [name]

Version number:**6.0**

Version date:**2022.03.01**

1. Program summary

Research topic:	To explore the treatment of optic neuromyelitis spectrum disease by electroacupuncture (NMOSD) Study on the efficacy and mechanism of pain in patients
Purpose of the research	Main purpose: to observe the electrical target NMOSD Secondary purpose of the curative effect of patient pain: Discussion NMOSD The mechanism of pain in patients and the mechanism of electroacupuncture in the treatment of pain in patients with optic neuromyelitis spectrum disease
Research hypothesis	Electroacupuncture can be treated effectively. NMOSD Pain in the patient
Research design	Randomized controlled trial
Test group	Electroneedle group
Control group	False needle group
Sample size	20
Selection Criteria	1 Accord with 2021 Diagnostic criteria for optic poliomyelitis genealogical diseases in China's Guidelines for the Diagnosis and Treatment of optic Neurospinal Myelitis Gene Diseases; 2 NRS \geq 4 Score; 3 Patients use stable doses of biotherapy and/or strong loose, before joining the group 30 There is no adjustment plan within the day; 4 Patients before joining the group 30 No standard drug combinations for pain treatment, including antiepileptic drugs, antidepressants or opioids, were adjusted within the day. 5 The patient or the patient's family sign informed consent. 6 18-80 Year-year-old patient.
Exclusion criteria	1 Patients participating in other clinical studies; 2 Patients with low cognitive or mental ability; 3 People who are pregnant, breastfeed or plan to get pregnant during the study; 4 People with serious diseases related to the heart, liver, kidneys or hematopoietic system; 5 Patients with diabetic peripheral neuropathy.
Test cycle	Total test cycle 30 God, all 18 Visit twice a week.
Outcome evaluation indicators	Main indicators: NRS Mark

	Secondary indicators:EDSS、MPQ Rating, SAS Anxiety Scale, SDS Depression Scale, SF-36 Quality of life scale, IL6、TNF-A、fMRI Target
Safety evaluation indicators	Adverse reactions, blood routine, biochemistry, liver function

2. Research background

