11.3.2 Report of serious adverse events

When there is a serious adverse reaction, it should be reported to Guangzhou University of Traditional Chinese Medicine within 24 hours of the second affiliated hospital and fill in the form of serious adverse events.

12. Data management and statistical analysis

Measurement data use: average \pm Standard deviation, median (M), maximum value, Minimum value, matching is used for comparison in the counting data group. T Test (Or pairing symbol rank sum test), variance analysis is used for inter-group comparison (non-normal distribution and variance irregularity are tested by rank sum (Kruskal-Wallis)) and two comparison and calculation 95% CI. The quantitative main outcome indicators of multiple observation time points are analyzed by repeated measurement. Rank sum test is used for comparison between hierarchical data groups (Kruskal-Wallis). The counting data is expressed by composition ratio and rate, and the comparison of total efficiency groups is expressed by cal-square test (or Fisher Accurate probability method). Intergroup composition Compared with comparison 2 \times C Table or 3 \times C Table cal-square inspection.

13. Confidentiality

The results of the research through this project may be published in medical journals, but we will keep the patient's information confidential in accordance with the requirements of the law. Unless required by relevant laws, the patient's personal information will not be disclosed. If necessary, government administrations and hospital ethics committees and their relevant personnel can consult patients' information as required.

14. Ethical standards

The program of this experiment, Case report form, The informed consent form should be approved in writing by the Ethics Committee of Guangdong Provincial Hospital of Traditional Chinese Medicine before it can be carried out.

The researcher or person authorized by the researcher will be responsible for explaining the benefits and risks of participating in the trial to each patient, the legal representative of the patient or notary witness, and shall obtain the patient's written informed consent during the screening examination.

All original informed consent co-signed and signed by the subjects or their legal representatives and the person presiding over the PIC process shall be kept by the researcher.

15. Study schedules

Starting and ending date	Main research content	Expected results

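### The primary outcome is named only as NRS: the protocol does not fix which NRS data or which treatment contrast decides the trial

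*Protocol*

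**What the plan says.** - **Primary outcome.** Section 1: "Main indicators: NRS Mark". Section 9: "Main evaluation indicators: NRS", followed by a garbled phrase about rating on a pain form. Neither place gives a time point, a source (visit or diary) or a derivation (level, change, mean).
- **Visit NRS.** Section 8 lists it at screening ("Perfect EDSS, NRS Scales, MPQ Pain scale, SDS Depression Scale, SAS Anxiety Scale, SF-36 Quality of life scale") and again after the last session ("Perfect EDSS, NRS Scales, MPQ Pain scale, SDS Depression Table, SAS Anxiety Scale, SF-36 Quality of life scale"), the latter at the "Eighth post-treatment visit (group No. 28 ± 3 Day" assessment.
- **Diary NRS.** Section 8, treatment period: "Patients fill in a pain diary every day". Section 7, under basic treatment: "Patients record the daily intake and intensity of analgesic drugs required. (NRS", followed by a reference to a standardised diary and the site of pain. The translation is poor, but intensity, NRS and diary stand together, so a daily NRS is the likely meaning.
- **Analysis.** Section 12 assigns between-group comparison of measurement data to ANOVA, or Kruskal-Wallis when normality or equal variance fails. For the main outcome it adds: "The quantitative main outcome indicators of multiple observation time points are analyzed by repeated measurement". It does not say which time points are meant or which model term is tested.
- **Size.** Section 6.1 sets 20 patients and calls the study exploratory. No alpha, SD, effect size or power is given.

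**The concern.** Section 12's repeated-measures sentence can be applied to the two visits or to about 30 diary days. Its ANOVA provision can be applied to the post-treatment visit score, to the change between visits or to a diary summary. Each is a defensible reading of the same text, and each gives its own p-value. Two things are at stake. If the choice is made after the data are seen, a nominal 5% test no longer has a 5% error rate. And one of the readings, a group main effect over screening and day 28±3, mixes a pre-treatment score into the treatment comparison and loses much of the power that 20 patients can offer.

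**Working it through.** The protocol has no figure to reproduce on this point: the sample size of 20 comes without inputs. Everything below rests on these assumptions: 10 patients per arm (simple randomisation does not guarantee it), two-sided alpha 0.05, and the SDs and correlations stated.

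**1. False positives if the most favourable reading is chosen.** Null trials were simulated with integer NRS scores on 0-10 and no difference between arms.

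- *Setting A* (between-patient SD 1.5, within-patient SD 1.2, AR(1) correlation 0.5 between days; 6,000 trials). Taking the smallest p over post-treatment visit score, change between visits and diary mean gave p < 0.05 in 11.1-11.8% of trials over repeated runs. Adding the diary slope gave about 15%.
- *Setting B* (SD 1.8, patient-level correlation 0.3, 0.5 or 0.7, AR(1) 0.7, screening NRS at least 4, same improvement in both arms; 4,000 trials each). Two readings (day-28 visit or last-week diary mean) gave 7.7-8.4%. The same three readings as in A gave 11.8-12.8%.

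Each of these readings tested alone stayed near 5%, so the excess comes from the choice and not from any one test. Three fully independent tests would give 1 − 0.95³ = 14.3%.

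**2. Power of the candidate contrasts.** Let the true difference at day 28±3 be d = 1.0 SD, with no true difference at screening, equal variances at both visits, and correlation r between visits. The standardised effect for each contrast is:

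- post-treatment score alone: d = 1.0
- group main effect over two visits: (d/2) / √((1 + r)/2)
- group-by-time, which with two visits is the change score: d / √(2(1 − r))
- ANCOVA on the screening score: d / √(1 − r²), with 17 degrees of freedom, ignoring chance baseline imbalance

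| Contrast | r = 0.3: effect, power | r = 0.7: effect, power |
|---|---|---|
| Post-treatment score alone | 1.00, 56% | 1.00, 56% |
| Group main effect, two visits | 0.62, 26% | 0.54, 21% |
| Group-by-time (change) | 0.85, 43% | 1.29, 78% |
| ANCOVA | 1.05, 60% | 1.40, 84% |

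Averaging halves the raw difference from 1.0 to 0.5 SD. The SD of the average shrinks only to 0.81 (r = 0.3) or 0.92 (r = 0.7), which does not make up for it.

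**3. The diary as primary.** With equal correlation r between days, a 7-day mean has variance ratio (1 + 6r)/7, which is 0.571 at r = 0.5 and 0.829 at r = 0.8. Power at d = 1.0 is then 80% and 64%. Under Setting A, the 7-day mean of the within-patient part has variance 1.44 × 17.03/49 = 0.50. The ratio is (2.25 + 0.50)/(2.25 + 1.44) = 0.745 and power is 69%. If the effect averaged over that week is only 85% of the effect at the final visit, power falls to 55%, no better than the single visit score.

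**The case against.** The strongest reply is that the natural reading is already clear. The NRS scale sits among the formal visit assessments, there is only one post-treatment visit, and the garbled words after NRS in Section 9 may point to that form. The diary is not listed as an outcome. It is introduced beside analgesic intake and may serve medication monitoring, and its NRS content rests on a poorly translated sentence. A figure and the technology roadmap are missing from the available text. An unseen SAP may fix the model, the ANOVA-to-rank switch is a stated rule, and the study is labelled exploratory.

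Much of this stands and sets the limits of the point. It does not remove it. Even if only the visit NRS counts, the protocol does not say whether level or change is compared or which repeated-measures term decides. The definition of the primary variable belongs in the protocol, whatever an SAP adds. The exploratory label softens the consequence, but Section 1 states an efficacy hypothesis tested against a sham control.

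Several stronger inferences are tempting and are not supported:

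- *The sections contradict each other on the endpoint.* They leave it open; none names a conflicting primary variable.
- *The diary goes unused.* Nothing says so, and the repeated-measures sentence may be meant for it.
- *The planned repeated-measures analysis halves the effect.* This holds only for the group main effect over two visits. The group-by-time effect halves nothing.
- *The diary mean should be primary because it brings power to 80%.* That figure needs a day-to-day correlation of 0.5 with equal correlation across days and a full effect all week. The choice between diary and visit is a trade-off.

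**Conclusion.** The point holds as an undefined primary variable and deciding contrast. If the reading were chosen after seeing the data, the false-positive rate would be about 11-13% for three readings instead of 5%. This describes what the wording permits and does not predict what the investigators will do. If the group main effect over the two visits were used, power at a 1.0 SD difference would be about 21-26%, against 56% for the post-treatment score alone. All of these figures depend on assumed SDs, correlations, alpha and equal arms, none of which the protocol gives. The direction of the conclusion does not depend on the exact values. The protocol should be amended, although the design itself can stay as it is.

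**What to change.** In Sections 1 and 9, name one primary variable: by default, the NRS at the post-treatment visit (day 28±3). In Section 12, state that it is compared between arms by ANCOVA with the screening NRS as covariate, reported as one treatment effect with its 95% CI. Declare all other NRS analyses secondary, including the last-7-day diary mean, the diary trajectory and any repeated-measures model.

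At a 1.0 SD difference with 10 per arm, this gives about 60-84% power for a visit correlation of 0.3-0.7, using a screening score that is already collected. The last-7-day diary mean is an acceptable alternative primary if the sponsor prefers it. It would need a rule for incomplete diaries, and its gain in precision depends on correlations the protocol does not give and on the effect being present throughout that week.

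The cost is a wording change and one degree of freedom for the covariate. No visit, measurement or treatment changes.
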